	progression at 6 months. Three Interim Analyses (IA) are planned for this study. The first IA will be performed after at least patients receiving alpelisib plus fulvestrant (cohort A) have at I t 6 months of follow-up.
	A second IA will be performed when approximately patients have been treated in the study (regardless of cohort) and have at least 6 months of follow-up on study. A third IA will be performed after the Core Phase has ended.
	The first two interim analyses will be performed to report preliminary efficacy (ORR, CBR) as well as key safety data in a descriptive fashion to provide additional information in this patient population. The third interim analysis will be performed to report all efficacy and safety data up to the end of the Core Phase.
	The final analysis will be performed after LPLV of the study which include cumulative data (eg safety and clinical benefit) since the Core Phase analysis.
	The primary efficacy analysis will be performed using modified full analysis set (mFAS). The modified Full Analysis Set (mFAS) comprises all patients of the FAS population who have PIK3CA mutation confirmed by a Novartis designated laboratory. The assessment of safety will be based mainly on the frequency of adverse events and laboratory values that fall outside of predetermined ranges.
Key words	HR+, Human Epidermal Growth Factor Receptor 2 (HER2)- negative, advanced breast cancer, alpelisib, fulvestrant, letrozole, Phosphoinositol 3-kinase-related-kinases (PI3K), Gene encoding p110alpha catalytic subunit of PI3K (PIK3CA) mutant, Phase II, CDK 4/6 inhibitor, men, pre and postmenopausal, aromatase inhibitor, endocrine therapy

Protocol No. CBYL719X2402

1 Background

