2.1 Data analysis general information

The final analysis will be performed by Novartis and/or a designated CRO. SAS version 9.4 or later software will be used to perform all data analyses and to generate tables, figures and listings.

Data included in the analysis

The analysis cut-off date for the first interim analysis of study data will be established after at least **CCI** patients receiving Alpelisib + Fulvestrant (cohort A) have at least 6 months of follow-up. The analysis cut-off date for the second interim analysis of study data will be established after at least **CCI** patients have been treated (regardless of cohort) and have at least 6 months of follow-up on study. The third IA will be performed after the Core Phase has ended.

The analysis cut-off date for the primary analysis of each cohort will be established 6 months after the last patient enrolled in that cohort has started treatment. The final analysis will be performed after LPLV of the study which include cumulative data (eg safety and clinical benefit) since the start of Core Phase for the patients who enter the Extension Phase.

All statistical analyses will be performed using all data collected in the database up to the data cutoff date. All data with an assessment date or event start date (e.g. vital sign assessment date or start date of an adverse event) prior to or on the cut-off date will be included in the analysis. Any data collected beyond the cut-off date will not be included in the analysis and will not be used for any derivations.

All events with start date before or on the cut-off date and end date after the cut-off date will be reported as 'ongoing'. The same rule will be applied to events starting before or on the cut-off date and not having documented end date. This approach applies, in particular, to adverse event and concomitant medication reports. For these events, the end date will not be imputed and therefore will not appear in the listings.

General analysis conventions

Pooling of centers: Unless specified otherwise, data from all study centers will be pooled for the analysis. Due to expected small number of patients enrolled at centers, no center effect will be assessed. Protocol deviations, number of patients in analysis populations and discontinuations from study treatment will be summarized by country.

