2.7.1 Secondary endpoints

The mFAS will be used for the secondary efficacy analyses.

Progression free survival

Secondary endpoints include PFS, defined as the time from the date of start of treatment to the date of the first documented progression or death due to any cause. PFS will be based on local investigators review of tumor assessments and using RECIST 1.1 criteria (see Appendix 5 of the study protocol). If a patient has not progressed or died at the analysis cut-off date, PFS will be censored at the date of the last adequate tumor evaluation date before the cut-off date. PFS events documented after the initiation of new anti-neoplastic therapy (i.e. RECIST 1.1 documented disease progression or death) will be considered for the primary analysis provided tumor assessments continue after initiation of new cancer therapy. Discontinuation due to disease progression (collected on the 'End of treatment' and 'End of post treatment follow up' disposition pages) without supporting objective evidence satisfying progression criteria per RECIST 1.1 will not be considered disease progression for PFS derivation. Clinical deterioration will not be considered as a qualifying event for progression.

Overall response rate

ORR is defined as the proportion of patients with best overall response (BOR) of complete response (CR) or partial response (PR) according to RECIST 1.1 (see Appendix 5 of the study protocol). ORR will be calculated based using local investigators review of tumor assessment data in patients with measurable disease at baseline. Patients with only non-measurable disease at baseline will be part of the analysis and will be included in the numerator only if a complete response was observed. Tumor assessments performed before the start of any further antineoplastic therapy (i.e. any additional secondary antineoplastic therapy or surgery) will be considered in the assessment of BOR.

Clinical benefit rate (CBR)

CBR is defined as the proportion of patients with a best overall response of CR or PR, or an overall lesion response of stable disease (SD) lasting 24 weeks or longer or Non-CR/ Non-PD lasting 24 weeks or longer, according to RECIST 1.1 criteria. A patient will be considered to have SD for 24 weeks or longer if a SD response is recorded at 23 weeks or later from

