2.7.2 Statistical hypothesis, model, and method of analysis

PFS

The survival distribution of PFS will be estimated using the Kaplan-Meier method. The results will be plotted graphically (Kaplan-Meier curves) by cohort. The plots will display the number of patients at risk at equidistant time points. The median, 25th and 75th percentiles for PFS for each cohort will be provided with associated 95% confidence intervals ([Brookmeyer and Crowley 1982](#)). The survival probabilities at 6, 12, 18 months, and the associated 95% confidence intervals will be summarized by cohort. Kaplan-Meier estimates will be obtained using PROC LIFETEST with method=KM option in SAS. The loglog option available within PROC LIFETEST will be used to compute the confidence intervals.

ORR and CBR

ORR and CBR will be calculated based on the mFAS. ORR and CBR will be summarized using descriptive statistics (N, %) separately for each cohort along with two-sided exact binomial 95% CIs [Clopper and Pearson 1934]. As sensitivity analysis, CBR will be calculated and summarized for patients with only measurable disease at baseline.

Duration of Response

DOOR will be listed and summarized by cohort for all patients in the mFAS with confirmed BOR of CR or PR. The distribution of time to response will be estimated using the Kaplan-Meier method and the median time to response will be presented along with 95% confidence interval only if a sufficient number of responses is observed. A responders-only analysis will also be performed in this case.

OS

OS will be analyzed in the mFAS population. The distribution of OS will be estimated using the Kaplan-Meier method. The median OS along with 95% confidence intervals will be presented for each cohort.

PFS2

PFS2 will be analyzed in the mFAS population. The PFS2 distribution will be estimated using the Kaplan-Meier method, and the Kaplan-Meier curves, medians and 95% confidence intervals of the medians will be presented separately for each cohort.

Extension Phase Clinical Benefit

Proportion of patients with clinical benefit as assessed by the investigator will be summarized at scheduled visits. Clinical benefit will be summarized using the Safety Set in Extension Phase.

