New anticancer therapy given prior to protocol defined progression	Ignore the new anticancer therapy and follow situations above	As per above situations
Death before first PD assessment	Date of death	Progressed

ORR

Patients with unknown or missing best overall response (BOR) will be counted as failures. If there is no baseline tumor assessment, all post-baseline overall lesion responses are expected to be 'Unknown'. If no valid post-baseline tumor assessments are available, the best overall response must be "Unknown" unless progression is reported. For the computation of ORR, these patients will be included in the mFAS and will be counted as 'failures'.

PFS 2

For PFS2, refer to [Table 2-6](#) for censoring and event date options and outcomes.

Table 2-6 Outcome and event/censor dates for PFS2 analysis

Situation	Event/Censoring Date	Outcome
No baseline assessment	Date of start of treatment	Censored
Progression or death during the next-line therapy	Date of progression (or death)	Event
Death prior to initiation of next-line therapy	Date of death	Event
No progression (or death) during the next-line therapy and no second new anti-neoplastic therapy is initiated	Last contact date	Censored
No progression (or death) during the next-line anticancer therapy and a second new anti-neoplastic therapy is initiated	End date of the next-line therapy	Censored
No next-line therapy initiated with patient known to be alive	Last contact date	Censored

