2.14 Interim analysis

The first Interim Analysis (IA) is planned after at least **CCI** patients receiving alpelisib plus fulvestrant (cohort A) have at least 6 months of follow up. Once **CCI** patients will be recruited, the interim analysis data cutoff will be the last patients first visit plus 6 months. The second IA is planned after **CCI** patients have been treated (regardless of cohort) and have at least 6 months of follow-up on study. The third IA will be performed after the Core Phase has ended.

At the time of the first two IAs, preliminary efficacy (ORR, CBR) as well as key safety data will be analyzed in a descriptive fashion. The primary endpoint will not be analyzed and no statistical hypothesis will be tested.

The third IA will include all efficacy and safety data up to the end of the Core Phase.

Primary endpoint will not be analysed and no formal statistical hypothesis testing will be done at the time of IA and therefore no multiplicity adjustment will be made.

Preliminary efficacy as well as key safety data will be analysed in a descriptive fashion separately in each cohort.

The following endpoints will be summarized at the time of the first two IAs:

- Overall response rate (ORR)
- Clinical Benefit rate (CBR)
- Average daily dose, cumulative dose, relative dose intensity
- Duration of exposure
- Dose reduction/interuptions
- Adverse events
- Serious adverse events
- Deaths
- Adverse event of special interest (AESI)
- Laboratory parameters

3 Sample size calculation

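### No efficacy set is named for the first two interim analyses; under the SAP's general rules interim CBR, and to a lesser extent ORR, is biased low

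*Protocol*

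**What the plan says.** **Timing.** The second interim takes place once a redacted number of patients "have been treated in the study (regardless of cohort) and have at least 6 months of follow-up on study" (protocol summary, Data analysis). Protocol 10.7 adds that this number is 50% of enrolled patients. The first takes place once a redacted number of "patients receiving Alpelisib + Fulvestrant (cohort A) have at least 6 months of follow-up" (SAP 2.1). For that one SAP 2.14 adds that "the interim analysis data cutoff will be the last patients first visit plus 6 months".

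**Content.** SAP 2.14 lists ORR and CBR among the endpoints of both interims and states: "Preliminary efficacy as well as key safety data will be analysed in a descriptive fashion separately in each cohort". It names no analysis set and no minimum follow-up.

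**General rules that then apply (SAP Amendment 4).**
- SAP 2.1: "All statistical analyses will be performed using all data collected in the database up to the data cutoff date".
- SAP 2.7.2: "ORR and CBR will be calculated based on the mFAS". The mFAS (SAP 2.2) is every dosed patient whose mutation was confirmed by the designated laboratory. Neither its definition nor Table 2-2 excludes a patient for short follow-up.
- SAP 2.7.1, for CBR: "A patient will be considered to have SD for 24 weeks or longer if a SD response is recorded at 23 weeks or later". Non-CR/Non-PD has the same 23-week requirement.
- SAP 2.7.3, for ORR: "Patients with unknown or missing best overall response (BOR) will be counted as failures". These patients stay in the denominator.

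Scans are every 12 weeks, plus or minus 7 days (protocol 7.2.1.1). Table 7-1 asks for a response to be confirmed at least 4 weeks later. No pause in enrolment is described.

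**The concern.** The 6-month condition decides when the analysis happens. Nothing carries it into who is analysed. While the trigger patients complete their 6 months, enrolment goes on, and each newly dosed patient with a confirmed mutation joins the mFAS. Such a patient adds one to the denominator before being able to add one to the CBR numerator as stable disease.

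The error can only be downward. It depends on accrual speed just before the cut-off, and it differs by cohort because results are shown cohort by cohort. Reporting preliminary ORR and CBR is the stated purpose of these two analyses, so the distortion falls on the figures they were added to provide.

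**Working it through.** **The plan's own figure.** The documents give no interim ORR or CBR. The design figure they do give reproduces. For N = 112, exact binomial, P(X ≥ 44 | 0.30) = 0.0225 and P(X ≥ 44 | 0.45) = 0.9055. The exact lower limit is 30.2% for 44/112 and 29.4% for 43/112. The interims test nothing, so this stays as it is.

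**1. What a patient can contribute, by time from first dose to cut-off**

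| Time since first dose | ORR | CBR |
|---|---|---|
| Under 12 weeks | no scheduled scan yet: failure | cannot count |
| 12-16 weeks | only an unconfirmed response is possible | same |
| 16-23 weeks | confirmed responders count | confirmed responders count; stable disease does not |
| 23 weeks or more | can count | can count |

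SAP 2.7.1 counts the 23 weeks for SD from enrolment, which may precede first dose. This changes little, because no scan is scheduled between weeks 13 and 23.

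**2. Accrual, from the amendment rationales**
- 30 patients (02-May-2018) to 127 (22-Jan-2019): 97/265 days = 0.366 per day (2.6 per week).
- 127 to 254 (08-Oct-2019): 127/259 days = 0.490 per day (3.4 per week).
- 254 to 380 (14-Dec-2020): 126/433 days = 0.291 per day.

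**3. Second interim, assumed trigger 170 (50% of 340)**

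Six months = 6 × 30.4375 = 182.6 days.

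At a constant rate r, the share under 24 weeks is 168r / (170 + 182.6r):
- r = 0.366: 61.5/236.8 = 26%
- r = 0.490: 82.4/259.6 = 32%

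Interpolating the actual counts puts patient 170 in April 2019 and the cut-off at about 19-Oct-2019, with about 257.3 enrolled:
- under 6 months: 87.3 (34%)
- under 23 weeks: 76.7 (30%)
- under 16 weeks: 52.7
- under 12 weeks: 38.9 (15%)

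**4. Reported rates, assuming true CBR 45% and true ORR 20%**
- CBR, no early responders counted: 0.45 × (257.3 − 76.7) / 257.3 = 31.6%.
- CBR, counting confirmed responders at 16-23 weeks (76.7 − 52.7 = 24.0 patients): (81.3 + 0.20 × 24.0) / 257.3 = 33.5%.
- ORR, confirmation required: 0.20 × (257.3 − 52.7) / 257.3 = 15.9%.
- ORR, first scan sufficient: 0.20 × (257.3 − 38.9) / 257.3 = 17.0%.

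A simulation at the first two accrual rates (Poisson accrual, exponential PFS with 45% progression-free at week 24, 20% potential responders) has a full-follow-up CBR of 48% and reports 34-37%. Its ORR is not used here, because the model lets responders progress as fast as everyone else.

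**5. Other assumed triggers**

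| Second-interim trigger | Under 6 months | Reported CBR (true 45%) | Reported ORR (true 20%) |
|---|---|---|---|
| 100 | 45% | 27-29% | 14-15% |
| 170 | 34% | 32-34% | 16-17% |
| 190 | 29% | 34-35% | 17-18% |

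For the first interim, an assumed trigger of 20-60 patients with Cohort A taking 50-100% of accrual gives 42-75% under 6 months. Reported CBR is then about 14-30% and ORR about 10-16%, against the same true rates.

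**6. Cohort C.** It entered with Amendment 3 (30-Jan-2019). To a cut-off of 19-Oct-2019 is 262 days. With even accrual from the amendment date, 168/262 = 64% of Cohort C would have under 24 weeks (76% for a trigger of 150, 55% for 190).

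**7. First cut-off.** If 'first visit' meant screening, up to 21 days before dosing, the last trigger patient would have 182.6 − 21 = 161.6 days (23.1 weeks) on treatment. The week 23-25 window runs from day 161 to day 175. If it means Cycle 1 Day 1, there is no shortfall.

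**The case against.** **The SAP nowhere states that the interims use every dosed patient.** A reader might infer a stated rule, but SAP 2.14 is silent and the full mFAS follows only from the general sections. Analysing only the trigger patients is a possible reading. This stands, so the defect is an unnamed set. The only set written down for ORR and CBR is still the mFAS, and applying it gives a low figure.

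**Not every recently dosed patient is a failure.** A reader might infer so. Patients at 16-23 weeks with a confirmed response count for both rates, which is why ORR suffers less than CBR.

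**The trigger patients need not fall short of 6 months on treatment.** That inference requires 'first visit' to mean screening. The term is undefined, and the trigger itself asks for 6 months of follow-up in patients receiving treatment. Only the ambiguity stands.

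**Nothing is decided on these figures.** The first two interims are descriptive, leave out the primary endpoint and have no stopping or adaptation rule. Duration of exposure is reported beside them, the study is non-comparative, and later analyses supersede them. This limits the harm to interim reporting but does not make the rates correct.

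**The triggers have passed.** Enrolment was complete as of 14-Dec-2020 and SAP Amendment 4 is dated 24-Mar-2022, so any 6-month trigger was reached by about mid-2021. The SAP versions of December 2018 and November 2019 are not in the documents. This stands, and it makes disclosure the more useful remedy.

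**The size is not established.** This also stands. Trigger counts are redacted, true rates are assumed, and enrolled counts stand in for the mFAS.

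**Conclusion.** The point holds as a gap in SAP 2.14 with a known direction. With no interim efficacy set named, the general rules bias interim CBR low, and ORR less so, most in the cohort enrolled latest.

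The illustration for the second interim (26-32% of dosed patients under 24 weeks; CBR of 45-48% reported as about 32-37%) rests on an assumed trigger of 170, the protocol's accrual counts and assumed true rates. Other triggers change the size and leave the direction the same.

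A reader might go on to doubt the trial's main result. The documents do not support that. Alpha, power and the 44-of-112 rule are untouched. The primary analysis waits until 6 months after each cohort's last patient starts, and the third interim follows the end of the Core Phase, 18 months or more after the last patient's first treatment.

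**What to change.** In SAP 2.14, for the first two interims:

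- Calculate ORR and CBR in mFAS patients first dosed long enough before the cut-off for the week 23-25 scan window to have closed, about 25-26 weeks. Define this by calendar time since first dose, whatever follow-up was achieved, so that early deaths and drop-outs stay in.
- Report, per cohort, how many mFAS patients are not yet evaluable, and give the all-mFAS result as supportive.
- Keep all dosed patients in the safety summaries.
- Date the first cut-off from the last trigger patient's first treatment, which removes the ambiguity of 'first visit'.

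If the interims have already been run, state in the study report which denominator was used and how many patients per cohort were not yet evaluable.

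The cost is SAP wording, a short disclosure and smaller interim efficacy denominators: in the illustration, about 170-174 in place of about 257. With the cut-off dated from first treatment, no trigger patient is lost, since 6 months is 26.1 weeks.

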1.1 Overview of disease pathogenesis, epidemiology and current treatment

1.1.1 Hormone receptor-positive breast cancer

Breast cancer (BC) is the most common cancer in women. It is estimated that more than 1.7 million new cases of breast cancer occurred among women worldwide in 2012 (GLOBOCAN 2012). It is estimated that worldwide over 508,000 women died in 2011 due to breast cancer (Global Health Estimates, WHO 2012). In 2014, an estimated 232,670 new cases were diagnosed in women in the United States; of those, 133,310 were in women < 65 years old. Fewer than 5% of breast cancers occur in women < 40 years old (American Cancer Society 2014), but it is still the leading cause of cancer death among women 20 to 59 years old (Siegel 2014). Breast cancer in men is a more rare disease and makes up < 1% of all cases of breast cancers, but its treatment is based on the guidelines for female breast cancer (Foerster 2014, Agrawal 2007, Patten 2013, Giordano 2002). Subtypes of invasive breast cancer are distinguished by expression of estrogen receptors (ER), progesterone receptors (PgR) and human epidermal growth factor receptor-2 (HER2), as well as by distinct gene expression profiles (Perou 2000; Sotiriou and Pusztai 2009). Within these subtypes, 60-70% of breast tumors are HR+, HER2-negative. Expression of the ER and/or PgR is one of the most important prognostic factors in invasive breast cancer. Estrogen deprivation therapy is the core treatment modality in patients with HR+ advanced breast cancer. Endocrine therapy options for postmenopausal women with ER+ advanced breast cancer (locally advanced, recurrent, or metastatic breast cancer (mBC)) including selective ER modulators (SERM; tamoxifen), ER antagonists (fulvestrant), selective nonsteroidal AIs (NSAI; anastrozole and letrozole) and steroidal aromatase inhibitors (AIs; exemestane). Blocking estrogen signaling with tamoxifen has been the main approach in treatment for ER+ breast cancer for over 35 years, especially in pre-menopausal women. In postmenopausal women, AIs reduce peripheral estrogen synthesis by blocking the conversion of androgens to estrogens in non-ovarian tissues; synthesis in these tissues is the primary source of estrogens in postmenopausal women. Als are generally used as the first line of therapy for women with HR+ breast cancer (Beslija 2009; NCCN 2017). In those patients that progress the combination of targeted agent and endocrine therapies have also been evaluated in the Bolero-2 trial: everolimus, a (Mammalian Target of Rapamycin (mTOR) inhibitor, combined with exemestane showed synergistic inhibition of the tumor proliferation and is approved for postmenopausal women with advanced HR+, HER2- negative breast cancer (advanced HR+ BC) in combination with exemestane after failure of treatment with letrozole or anastrozole demonstrating progression survival improvement (Baselga 2012; Yardley 2014).

Recent data have noted that cell cycle related genes and proteins are frequently dysregulated in breast cancer. Cyclin D kinases inhibitors have been introduced with palbociclib, a Cyclin-Dependent Kinase 4 and 6 inhibitor (CDK4/6i) now approved in United States in combination with letrozole for the treatment of postmenopausal women with ER+, HER2-negative advanced breast cancer as initial endocrine-based therapy for their metastatic disease based on the results of a phase II Paloma-1 study (Finn 2015). Recently, palbociclib in combination with an AI was approved in EU in the similar population based on the phase 3 Paloma- 2 study (Finn 2016) in which the addition of palbociclib to letrozole resulted in a median PFS of 24.8 months vs 14.5

months in letrozole alone. Furthermore, a Phase III study of palbociclib in combination with fulvestrant in second line HR+ mBC patients (Paloma-3) demonstrated significant improvement in PFS versus fulvestrant alone (9.5 months vs 4.6 months) (Cristofanilli 2016). Ribociclib is another CDK 4/6 inhibitor, recently approved in both United States and Europe in HR+, HER2-negative post-menopausal patients with advanced breast cancer. MONALEESA-2, a Phase III study of ribociclib in combination with letrozole in the first line aBC setting met its primary endpoint early at a pre-defined interim efficacy analysis, demonstrating a statistical and clinically meaningful benefit in PFS with the combination compared with letrozole alone (Hazard Ratio=0.556; 95% CI, 0.429, 0.720; p=0.00000329x 10⁶) (Hortobagyi 2016). Recent updates demonstrated continued benefit for patients with combination with PFS at 25.3 months compared with 16.0 months in letrozole alone group (Hazard Ratio=0.568; 95% CI,0.457-0.704; p=9.63x10-8) (Hortobagyi 2017).

Another CDK4/6 inhibitor, abemaciclib, also demonstrated clinical efficacy in same population in MONARCH-3 study, results showed a statistical and clinical meaningful improvement in PFS with combination arm with anastrozole or letrozole compared with letrozole alone (Hazard Ratio= 0.54, 95% CI, 0.41-0.72, p=0.000021) (Goetz 2017). Abemaciclib with Monarch -2 results also received FDA approval in post progression population on neoadjuvant/adjuvant or while post first line metastatic setting on endocrine therapy in combination on continuous daily dosing with fulvestrant 500 mg showing extended PFS benefit versus fulvestrant alone (median, 16.4 vs. 9.3 months; Hazard Ratio 0. 553; 95% CI, 0.449 to 0.681; p <0.001) (Sledge 2017).

